12.6 Secondary Analyses

If the primary efficacy analysis is statistically significant, the key secondary endpoints, as identified in Section 10.1.2, will be analysed in hierarchical order, according to their order in Section 10.1.2. If the analysis of the first key secondary endpoint is statistically significant, then the hierarchical analysis will continue with analysis of the second key secondary endpoint. However, if the analysis of the first key secondary endpoint is not statistically significant, then the hierarchical analysis will stop after analysis of the first key secondary endpoint. This method will continue until either all of the key secondary endpoints have been analysed hierarchically or the analysis of one of the key secondary endpoints is not statistically significant, at which point the hierarchical analysis of key secondary endpoints will stop.

The non-key secondary endpoints will be analysed inferentially, but not hierarchically.

12.6.1 Efficacy Endpoints and Analyses (Secondary)

Key Secondary Endpoints

- A composite of the proportion of patients with hospitalisation or death related to major complications of device implantation (i.e., need for thoracotomy, pericardiocentesis, or vascular surgery) or complications of long-term device therapy (i.e., infection not leading to hospitalisation, lead and/or generator removal/replacement, inappropriate shocks, explantation). This endpoint will be analysed for superiority. These proportions will be compared between the patients with $H/M \geq 1.60$ in the AdreView™ group and the patients with $H/M \geq 1.60$ in the SoC group, using the Cochran-Mantel-Haenszel test stratified by enrolling centre, using a 2-sided alpha value of 0.050.

- Cardiac death. The occurrence of this event will be analysed in the primary efficacy population using a Cox proportional hazards model as was performed in the primary efficacy analysis (non-inferiority [NI], using an NI margin of 1.20).
- Rate of hospitalisation for cardiovascular cause. This rate will be compared between the AdreView™ and SoC groups using the Miettinen and Nurminen methodology [\[Miettinen and Nurminen 1985\]](#), (non-inferiority [NI], using an NI margin of 1.20).
- Rate of all-cause hospitalisation. This rate will be compared between the AdreView™ and SoC groups using the Miettinen and Nurminen methodology [\[Miettinen and Nurminen 1985\]](#), (NI, using an NI margin of 1.20).
- A composite of the occurrence of resuscitated life-threatening ventricular tachycardia, unstable ventricular tachy-arrhythmias, SCD and resuscitated cardiac arrest. The occurrence of this event will be analysed in the primary efficacy population using a Cox proportional hazards model as was performed in the primary efficacy analysis (non-inferiority, using an NI margin of 1.20).

Additional Secondary Endpoints

- Syncope. The occurrence of this event will be analysed in the primary efficacy population using a Cox proportional hazards model as was performed in the primary efficacy analysis (non-inferiority, using an NI margin of 1.20).
- Clinical and healthcare resource utilisation data collected in this study including ICD implantation, all hospitalisations, treatment of AEs, and AdreView™ administration will be used in an economic evaluation of study outcomes for relevant geographies. These clinical and healthcare resource utilisation data will be summarised in the primary efficacy population and compared between the AdreView™ and SoC groups. These data will be analyzed with a superiority analysis, using a 2-sided alpha value of 0.05. These data may also be used for future health economic analyses.
- A composite of the rate of hospitalisation and death related to major complications of device implantation (i.e., need for thoracotomy, pericardiocentesis, or vascular surgery) and a composite of the rate of complications of long-term device therapy (i.e., infection not leading to hospitalisation, lead and/or generator removal/replacement, inappropriate shocks, explantation). The occurrence of these events will be analysed in the primary efficacy population using a Cox proportional hazards model as was performed in the primary efficacy analysis between the AdreView group and the SoC group. These data will be analyzed with a superiority analysis, using a 2-sided alpha value of 0.05.

12.6.2 Exploratory Variables and Analyses

12.6.3 Safety Variables and Analyses

The safety variables to be analysed include all events occurring after informed consent, all AEs, including AdreView™-emergent AEs, SAEs, vital sign data, physical examination results, clinical laboratory test data, and electrocardiographic data. All safety analyses will be performed in the safety population.

All events occurring after informed consent and AEs will be summarised by MedDRA system organ class and preferred term (PT). An overall summary of AEs will be presented. AdreView™-emergent AEs will also be presented by causal relationship to study drug. Summaries of SAEs, AdreView™-emergent SAEs and other significant AEs will also be presented.

For vital signs, clinical laboratory tests, ECG data, and baseline values will be summarised with descriptive statistics (mean, SD, median, minimum, and maximum) for each enrolment group. For vital signs, post-enrolment changes from baseline and shift tables of all post-administration changes from baseline versus time will also be generated for each cohort. In addition, potentially clinically significant values will be summarised for vital sign parameters. Physical examination data will be presented by enrolment group and time point. All safety data will be listed by enrolment group and patient number.

Safety variables will also be transmitted regularly to the independent statistician of the DSMB for their regular safety assessment as per the DSMB charter,

12.6.3.1 Clinical Laboratory Evaluation

Clinical laboratory tests will be performed at only the screening/enrolment visit. Descriptive statistics will be displayed for the observed values and changes from baseline.

Summarisation will be by cohort. In addition, all clinical laboratory data will be listed by enrolment group and patient number.

12.6.3.2 Vital Signs

Descriptive statistics will be displayed for the observed values and changes from baseline. For each vital-sign variable and each time point, the following safety endpoints will be summarised by counts and percentages.

- The occurrence of 1 or more changes from baseline, at each post-administration time point, greater than a pre-specified magnitude (20 mm Hg for systolic blood pressure, 10 mm Hg for diastolic blood pressure, 10 beats per minute for heart rate, 10 breaths per minute for respiratory rate).
- The occurrence of post-administration values outside the normal limits ([Table 3](#), Section [15.3](#)). Shift tables based on the normal range will be prepared.

All summarisations will be by enrolment group. In addition, all clinical laboratory data will be listed by enrolment group and patient number.

12.6.3.3 Electrocardiograms

Electrocardiograms will be performed at only the Screening/Enrolment visit. Descriptive statistics will be displayed for the observed values and changes from baseline. All summarisations will be by enrolment group. In addition, all ECG data will be listed by enrolment group and patient number.

12.6.3.4 Physical Examination

The number and percentage of patients with changes in physical examination status from normal at baseline (complete physical examinations) to abnormal at each post-randomisation (allocation) time point (brief physical examinations) (and vice versa) will be presented by cohort.

In addition, all physical examination data will be listed by enrolment group and patient number.

12.6.3.5 Adverse Events

All AEs occurring after informed consent will be recorded on the eCRF.

An overall summary of AEs will be presented, including the numbers of patients with any events occurring after informed consent, any AEs, any SAEs, any AdreView™-emergent AEs/SAEs, any causally related AdreView™-emergent AEs/SAEs, any severe AEs, any AEs leading to discontinuation of study drug, and any AEs leading to discontinuation from the study.

The number and percentage of patients with 1 or more AEs occurring after informed consent and the number and percentage of patients with 1 or more AdreView™-emergent AEs will be summarised by cohort, using MedDRA PTs and System Organ Classes. A patient will be counted only once within a System Organ Class or PT even if the patient experienced more than 1 event within a specific System Organ Class or PT.

The number and percentage of patients with AEs will also be summarised by maximum severity of AE (mild, moderate, or severe).

The number and percentage of patients with AEs will also be summarised by relationship to study drug. The Events eCRF page asks the following question: "Was there a reasonable possibility that the study drug caused the event?" with responses of "1 Yes, causal relationship is a reasonable possibility" or "2 No, causal relationship is not a reasonable possibility."

A summary of the number and percentage of patients with SAEs and AdreView™-emergent SAEs will also be presented by MedDRA System Organ Class and PT.

All AEs will be listed by enrolment group and patient number, and AdreView™-emergent AEs/SAEs will be flagged.

The Sponsor will also summarise other significant AEs, defined as laboratory abnormalities that qualify as such AEs (other than those meeting the definition for serious) and any events that led to an intervention (including premature discontinuation of AdreView™, dose reduction, or significant additional concomitant therapy), in addition to those reported as SAEs.

12.6.4 Resource Utilisation

Resource utilisation, including but not limited to ICD implantation, hospitalisation, treatment of AEs, and AdreView™ administration, will be analysed as detailed in Section [12.6.1](#).

12.7 Interim Analysis

The DSMB will perform a continuous monitoring of the safety of the study by regular analysis of safety data. This analysis will be done based on blinded data but the DSMB retains the right to request unblinding of the data after their safety review. The reasons for unblinding the data will be documented in the DSMB meeting minutes.

Additionally, during the course of the trial the DSMB may recommend to the ESC and Sponsor to perform the following interim analyses:

- An interim analysis for futility that will be conducted to verify the sample size assumptions and therefore the power of the study to achieve its objectives. Based on these results, DSMB may recommend to the ESC and Sponsor to re-calculate the sample size, prolong or terminate the study prematurely. The Sponsor will make the final decision. This interim analysis for futility will be performed using the methods of [\[Chen et al. 2004\]](#). The CRO, using unblinded data, will estimate conditional power and perform sample size re-estimation. The CRO will then give these analysis results to the independent statistician on the DSMB. Since this analysis is unblinded, there will be a small adjustment to the study's final alpha value.
- An interim analysis for efficacy. In that case, it could be conducted using the method described by [\[O'Brien et al. 1979\]](#), the 1-sided alpha value for the interim analysis for efficacy would be 0.0027.

12.8 Sample Size Calculation

Assumptions:

The all-cause mortality rate that is expected in the study has been estimated using the all-cause mortality rate observed in Study GE-122-016 at 36 months (internal report). It is assumed:

	Patients with $25\% \leq \text{LVEF} \leq 30\%$		Patients with $30\% \leq \text{LVEF} \leq 35\%$	
	%	Mortality Rate	%	Mortality Rate
H/M ratio <1.6	79%	20.25%	75%	15.14%
H/M ratio ≥ 1.6	21%	9.72%	25%	4.68%

In addition, the following observations or assumptions were taken: the ratio of patients with $25\% \leq \text{LVEF} \leq 30\%$ vs $30\% \leq \text{LVEF} \leq 35\%$ is expected to be 1:4 to account for the prior enrollment of only patients with $30\% \leq \text{LVEF} \leq 35\%$; the hazard ratio of patients with ICD implantation vs with usual care in the existing practice is 0.9 [Køber et al. 2016]. Referring to existing practice, only 15% of patients with $25\% \leq \text{LVEF} \leq 35\%$ currently receive ICD. Accordingly, the number of patients who currently do not receive ICD but who will receive it according to protocol and the number of patients who currently receive ICD and who will not receive it according to protocol have been calculated. In addition, the all-cause mortality rate of patients currently not receiving ICD but who will receive according to protocol (85% of patients with H/M ratio <1.6 in the AdreView™ group) has been corrected to take into account the 31% reduction in all-cause mortality observed at 20 months in the MADIT II trial [Moss et al. 2012]. These assumptions led to a composite mortality rate of 11.34% in the AdreView™ group and 13.33% in the SoC group. The sample size is estimated with the hypothesis of not having a relative increase of mortality rate in excess of 20% and with the following assumptions:

- Alpha = 0.025, 1-sided.
- Statistical power = 80%.
- 1:1 randomisation to AdreView™ and SoC groups.
- $H_0: \text{HR} \geq \text{HR}_0$ vs $H_1: \text{HR} < \text{HR}_0$. $\text{HR}_0 = 1.20$.
- Assumed HR: 0.84.
- Accrual time: 18 months.
- The total study duration: 48 months.
- AdreView™ group survival rate at 36 months: 0.887.

Based on the above assumptions, the required total number of events will be 247, and the required total number of randomized patients will be 2001.

The planned study accrual will be at least 2354 patients screened in order to randomize at least 2001 patients in the study.

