Name of Sponsor/Company: GE Healthcare Ltd. and its Affiliates	Individual Study Table Referring to Part of Dossier in Which the Individual Study or Study Table is Presented:	(For National Authority Use Only)
Name of Finished Product: AdreView™ (Iobenguane I ¹²³ Injection)	Volume:	
Name of Active Ingredient: I ¹²³ Iodine- meta- iodobenzylguanidine	Reference:	
to the SoC group will undergo ICD implantation and will be managed and followed up in accordance with internationally accepted HF guidelines.		
Patients will attend follow-up visits at the rate determined by the investigator, in accordance with their clinical standard practice. However, a follow-up visit must take place at least every 6 months (an extra follow-up visit will be performed at 3 months after ICD implantation). All patients will also attend an end-of-study visit.		
Selection of Patients:		
Inclusion Criteria:		
Patients may be included in the study if they meet all of the following criteria:		

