Patients with $25\% \leq \text{LVEF} \leq 35\%$, and meeting all other inclusion criteria and not meeting any of the exclusion criteria, will be randomly assigned to the AdreView™ group or the SoC group. All patients will be scheduled for an AdreView™ scan. The results of the AdreView™ scan in the SoC group will remain blinded to the investigator to avoid any influence in the decision of implanting an ICD. The results of the AdreView™ scan in the AdreView™ group will be known to the investigator and as such be used to assess their cardiovascular risk level and determine ICD implantation. Patients with AdreView™ H/M ratio < 1.6 (high 1- and 2-year mortality risk) will undergo ICD device implantation. Patients with AdreView™ H/M ratio

≥ 1.6 (low 1- and 2-year mortality risk) will continue to receive guideline-directed optimal medical therapy according to clinical standard practice medical therapy and will not undergo ICD implantation. Patients in this later group will undergo a second AdreView™ scan (planar and possibly SPECT) 2 years post-randomisation for purposes of re-stratification. Patients allocated to the SoC group will undergo ICD implantation and will be managed and followed up in accordance with internationally accepted HF guidelines.

Patients will attend follow-up visits at the rate determined by the investigator, in accordance with their clinical standard practice. However, a follow-up visit must take place at least every 6 months (an extra follow-up visit will be performed at 3 months after ICD implantation). All patients will also attend an end-of-study visit.

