The study will recruit patients with stable HF who have been under guideline-directed medical therapy for at least 3 months and have $25\% \leq \text{LVEF} \leq 35\%$. Patients will be randomised to one of the 2 following groups. In one group, AdreView™ imaging will lead the decision of whether or not to implant an ICD and in the other it will not (the AdreView™ scan result will not be disclosed to the investigator). AdreView™ is a diagnostic radiopharmaceutical approved in the USA and several European countries for the identification of HF patients, NYHA class II and III with lower 1- and 2-year mortality risk. Patients randomised to the AdreView™ arm will have an ICD implanted within 45 days of randomisation if they are deemed to be at high risk according to the definition in Section 6.1 (AdreView™ H/M ratio [measured on an anterior planar image obtained at 3 hours and 50 minutes post-injection and calculated according to the instructions in the Imaging Manual] lower than 1.6). These patients should then face the same risks and benefits as those managed according to guidelines in the regular clinical setting.

Patients considered to be at low risk by AdreView™ imaging (i.e., those with a planar image H/M ratio ≥ 1.6) will not receive an ICD, thus avoiding the exposure to complications; however they may face the risk that a potentially beneficial ICD implantation is withheld. GE Healthcare-sponsored study reports used for regulatory submissions (MBG311, MBG312 and MBG313; reports available upon request) have consistently showed a significant difference in all-cause and cardiac mortality between the high and the low risk groups in favour of the latter. These patients will also continue to receive the usual guideline-directed optimal medical therapy needed for their condition, including all the necessary follow-up visits and tests deemed necessary by the physician in charge. In addition, these patients will undergo a second AdreView™ H/M ratio determination 2 years after the first one in order to assess if their risk level has increased and ICD implantation is warranted. Moreover and as described in the protocol, the DSMB will regularly assess all safety aspects of the study.

Patients randomised to the SoC group will be treated in accordance to guidelines including having an ICD implanted, and therefore should then face the same risks and benefits as those managed according to guidelines in the regular clinical setting.

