- b Recorded up to 30 days before screening. Investigators should record all guideline-directed optimal medical therapy. Should any patients not be receiving guideline-directed optimal medical therapy at target dose per local guidelines, the investigator must document the reason(s) why in the source documents.
- c A serum or urine pregnancy test will be performed for all women of childbearing potential.
- d Before vital signs are measured, the patient should be resting for at least 5 minutes. The same arm and position will be used each time vital signs are measured for a given patient and blood pressure will be measured from the arm contra-lateral to the site of AdreView™ administration whenever possible.
- e Acceptable methods of LVEF assessment are radionuclide or contrast ventriculography, ECG-gated SPECT MPI, MR, CT, or 3D 2D echocardiography (Simpson's or multidisc method or equivalent only). Image files will be sent to the Sponsor.
- f AdreView™ will be administered to all patients. First AdreView™ administration should be performed in the 15 (+7) days post-randomisation. For the low-risk cohort only, a second AdreView™ administration should be administered at 2 years (± 30 days) post-randomisation, unless patient withdraws prior to study termination or has already received an ICD. In this case the second AdreView™ scan will be offered before withdrawal becomes effective. Thyroid blocking should be performed before administration of AdreView™ in accordance with the Package Insert/Summary of Product Characteristics/IB and local regulations unless the patient has had a complete thyroidectomy.
- g At 3 hours 50 minutes after administration of AdreView™, patients will undergo a 10-minute acquisition of planar images, and whenever possible followed by SPECT acquisition, according to the imaging manual. Patients with LVEF 25% to 35% with an H/M ratio ≥ 1.6 will have a second AdreView™ scan at 2 years (± 30 days) post-randomisation.
- h Patients in the randomised AdreView™ group who are assessed as high risk, and patients in the SoC group according to the standard of care in each investigational site derived from the local implementation of internationally accepted HF guidelines. ICD implantation should be performed according to clinical practice and should be performed within 45 days after randomisation.

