9.3 Post-Randomisation Procedures

All female patients (unless pre-menarchal, surgically sterile or post-menopausal) will undergo a serum or urine pregnancy test on the day of and prior to AdreView™ administration. AdreView™ dosing will only commence if the result is negative.

AdreView™ will be administered to all patients.

The first AdreView™ administration should be performed in the 15 (+7) days post-randomisation. Starting at 3 hours 50 minutes after administration of AdreView™, patients will undergo a 10-minute acquisition of anterior planar images of the thorax, and whenever possible these will be followed by a SPECT acquisition. Details of the acquisition and transmission of images to the Sponsor are provided in the study Imaging Manual.

Only those patients allocated to the AdreView™ arm will have the results of the scan (H/M ratio calculated on an anterior planar image obtained at 3 hours and 50 minutes for 10 minutes, and with regions placed following the standard quantification method according to the Imaging Manual) available to make a decision on the need for implantation of an ICD. In patients allocated to the SoC group, the investigator will remain blinded to the results of the AdreView™ images and any information derived from them in order not to influence the decision to implant or not implant an ICD.

Patients in the AdreView™ arm who are deemed at high-risk for all-cause and cardiovascular mortality (H/M ratio <1.6 as defined in Section 6.1) will undergo ICD device implantation. ICD implantation should be performed within 45 days of randomisation. Patients deemed to be at low risk (H/M ratio ≥ 1.6 as per Section 6.1) will continue to receive guideline-directed optimal medical therapy but will not undergo ICD implantation. In the low risk group, a second AdreView™ scan will be performed at 2 years following the first scan, or in case of early withdrawal, prior to this withdrawal being effective.

Patients randomly allocated to the SoC group will undergo ICD implantation and will be managed and followed up in accordance with internationally accepted HF guidelines. ICD implantation should be performed within 45 days of allocation to the SoC group. The results of the AdreView™ scan will remain blinded to the investigator to avoid any influence regarding patient management. AEs, SAEs and AdreView™-emergent AEs will be recorded.

All data related to primary and secondary endpoints will be collected.

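### The 80% power rests on 15% ICD use and two different ICD effects, but the design text has SoC patients implanted; with full uptake and one effect in both arms it is about 26–30%

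*Protocol*

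**What the plan says.** **Planning assumptions.** Protocol 12.8 takes 36-month mortality by LVEF band and H/M group from an earlier study and mixes the two LVEF bands 1:4. It then states: "Referring to existing practice, only 15% of patients with" LVEF 25–35% have an ICD. Two ICD effects are used. One is a hazard ratio of 0.9 for ICD against usual care in existing practice. The other applies to the 85% of AdreView H/M<1.6 patients who would be newly implanted, whose mortality "has been corrected to take into account the 31% reduction in all-cause mortality observed at 20 months in the MADIT II trial". The results are 11.34% mortality in the AdreView arm and 13.33% in SoC, an assumed hazard ratio of 0.84, and 247 events for 80% power against a margin of 1.20. The synopsis and SAP 2.3 repeat this.

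**SoC arm as described in the design.** The synopsis says that patients allocated "to the SoC group will undergo ICD implantation and will be managed and followed up in accordance with internationally accepted HF guidelines". Section 6.1 says "Patients allocated to the SoC group will undergo ICD implantation". Section 6.4 says "Patients randomised to the SoC group will be treated in accordance to guidelines including having an ICD implanted". Section 9.3 adds a time limit: "ICD implantation should be performed within 45 days of allocation to the SoC group". SAP 2.2 has the same rule.

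**Looser wording.** Table 1 footnote h has implantation for "patients in the SoC group according to the standard of care in each investigational site". Section 9.3 keeps SoC scans blinded "in order not to influence the decision to implant or not implant an ICD". The background (section 4) says that about half of the patients who meet guideline criteria get an ICD.

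**First key secondary endpoint.** Section 12.10 (repeated in SAP 2.3) assumes that 5–10% of SoC patients with H/M≥1.6 suffer harm from ICD implantation, against essentially none in AdreView patients with H/M≥1.6.

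No section states the ICD implantation rate assumed for the SoC arm of this trial.

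**The concern.** The power statement and the design text describe different control arms. At 15% ICD use, the AdreView strategy implants many H/M<1.6 patients whom SoC leaves without a device, so it can be expected to lower mortality. If SoC patients are implanted, H/M<1.6 patients are managed alike in both arms, and AdreView differs only by withholding the device in H/M≥1.6 patients. A mortality advantage of 16% is then hard to produce.

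The two ICD effects add a second difficulty. A 31% reduction credited to one arm and a 10% hazard reduction to existing practice builds an advantage into the AdreView arm that does not come from the imaging strategy.

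At stake is whether readers can take 80% as the planned power of the design described. The margin, the type I error and the analysis methods are not affected.

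**Working it through.** **1. The plan's own figures.** Events = 4(1.96+0.8416)²/[ln(0.84/1.20)]² = 246.8, so 247 is right. Power = Φ((√247/2)·ln(1.20/HR) − 1.96), which gives 80.0% at HR 0.84. The stated rates agree with that HR: ln(1−0.1134)/ln(1−0.1333) = 0.841.

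**2. What the SoC rate implies.** From the 12.8 table at a 1:4 mix, in percentage points of mortality:
- H/M<1.6: 0.2×0.79×20.25 + 0.8×0.75×15.14 = 12.28
- H/M≥1.6: 0.2×0.21×9.72 + 0.8×0.25×4.68 = 1.34
- total 13.63, of which 9.9% is in H/M≥1.6

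The stated SoC rate is 2.2% below this total (1−13.33/13.63) and the AdreView rate 16.8% below it. Applying 0.9 to 15% of patients gives 13.42%, close to 13.33%; applying it to all gives 12.26%. The SoC figure therefore reflects low uptake.

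**3. Full SoC uptake, same ICD effect in both arms.** Let e_hi and e_lo be the ICD mortality ratios in H/M<1.6 and H/M≥1.6. AdreView A = 12.28·e_hi + 1.34; SoC S = 12.28·e_hi + 1.34·e_lo; HR = ln(1−A)/ln(1−S).

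| e_hi | e_lo | A % | S % | HR | Power |
|---|---|---|---|---|---|
| any | 1.0 | equal | equal | 1.00 | 30% |
| 0.9 | 0.9 | 12.40 | 12.26 | 1.012 | 27% |
| 0.69 | 0.9 | 9.82 | 9.69 | 1.015 | 26% |
| 0.69 | 0.69 | 9.82 | 9.40 | 1.047 | 19% |

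Reading the table as mortality with every patient already implanted gives the same 19–30% range. At HR 1.00, 80% power would need about 945 events.

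**4. Harm in low-risk patients.** The documents give no ratio, so these are illustrative (e_hi 0.9 / 0.69): e_lo 1.10 gives 33% / 34%; 1.25 gives 38% / 40%; 1.50 gives 47% / 51%. HR 0.84 through low-risk harm alone needs e_lo of 2.62 / 2.31.

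**5. Full uptake with the plan's unequal effects.** SoC = 0.9×13.63 = 12.26%. AdreView, with 0.69 for 85% and 0.9 for 15% of H/M<1.6 patients, = 12.28×(0.85×0.69+0.15×0.9)+1.34 = 10.21%. HR = 0.82 and power = 84%. Other readings of the remaining 15% give 80–91%.

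**6. Partial uptake u, common effect.** S = 12.28·(1−u+u·e_hi) + 1.34·(1−u+u·e_lo), with A as in step 3. The lower figure takes e_lo = e_hi, the upper e_lo = 1.

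| Uptake | e_hi 0.9 | e_hi 0.69 |
|---|---|---|
| 15% | about 56% | about 96% |
| 50% | 44–45% | 79–83% |

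On the hazard scale with e_lo = e_hi, the figures are 53% and 95% at 15% uptake, and 42% and 76% at 50%. They are illustrative: 11.34% and 13.33% cannot be rebuilt from the listed inputs, which give about 10.4% and 13.4%.

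**7. Section 12.10 against 15% uptake.** If 15% of SoC H/M≥1.6 patients are implanted, harm in 5–10% of all of them means 0.05/0.15 = 33% to 0.10/0.15 = 67% per implanted patient. If instead 5–10% is taken as the rate per implant (an assumption), the SoC rate is 0.15×5–10% = 0.75–1.5%. With about 240 per arm, power is then about 11–49% by an uncorrected, unstratified Mantel-Haenszel test or 1–15% by Fisher's test, against the 80–90% used in planning.

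**The case against.** **SoC implantation may not be universal.** This stands. Footnote h, the open implantation decision in 9.3, the background's figure of about half, the mention of ICD crossover in 7.4.1 and the planned comparison of implantation rates in SAP 5.4.3.2 all leave room for less than full uptake. A reader might infer that the trial's true planned power was 19–30%. The documents do not support that: it is a conditional result for full uptake, and at 50% uptake with a 31% reduction power is close to the stated 80%.

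**Uptake alone does not cause the loss.** This also stands. Step 5 shows that the plan's own unequal effects keep about 84% at full uptake. The loss comes from full uptake together with equal effects. Equal effects are the more natural premise, since the same device is used in the same risk group, but they are my condition and not a statement in the plan.

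**The 19% end is weakly supported.** Agreed. It gives H/M≥1.6 patients a 31% reduction that 12.8 applies only to H/M<1.6, while 6.1 supposes that low-risk patients would not benefit. Hence 26–30% is the main range.

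**ICDs may harm low-risk patients.** Section 6.1 allows for this, and it raises power, but the ratio needed to restore HR 0.84 is above 2.3 and 12.8 does not invoke one.

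**The trial was stopped early.** True, and SAP 5.4.4 treats secondary results as reference only. This limits the consequence to the stated planned power.

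**Conclusion.** The concern holds as an inconsistency between assumptions. The event calculation is correct for HR 0.84, but the SoC arm described in the synopsis, 6.1, 6.4, 9.3 and SAP 2.2 does not lead to HR 0.84 once one ICD effect is used in both arms. With all SoC patients implanted, the expected HR is about 1.00–1.05 and power about 26–30%. It is 19% if low-risk patients share the full 31% reduction, and 33–51% for illustrative low-risk harm ratios of 1.1–1.5.

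A reader might also infer that keeping the 15% figure rescues the primary power and leaves only the first key secondary endpoint in trouble. That does not follow. At 15% uptake primary power runs from about 56% to 96% depending on which of the plan's two effects is taken as common, so 80% is not secured there either. The conflict between 15% uptake and 12.10 is separate, and the 33–67% figures need no assumption beyond that uptake.

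Confidence is high in the contradiction and in the full-uptake figures under their stated conditions. The figures at partial uptake are illustrative. The point should be fixed because it corrects a stated power; it changes no analysis.

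**What to change.** Reconcile the SoC implantation wording in the synopsis, 6.1, 6.4, 9.3, Table 1 footnote h and SAP 2.2 with the 15% figure. I take no view on which clinical rule is right.

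Then state one assumed SoC implantation rate and one ICD effect per risk group, the same in both arms, and use them in the synopsis, 12.8, 12.10 and SAP 2.3. Restate the expected hazard ratio, the power for 247 events and the power for the first key secondary endpoint, and show each at 15%, about 50% and 100% SoC uptake. Show how 11.34% and 13.33% were derived; otherwise mark the power at partial uptake as illustrative.

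The cost is wording and recalculated planning figures, with no new data. The downside is a less favourable stated power under several of these settings.
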